microRNA and Carbohydrate Metabolism Recently, a new class of small noncoding RNAs, termed microRNA, has been identified as critical regulators of energy homeostasis and carbohydrate metabolism (13). Through negative inhibition, microRNA can influence molecular processes by binding to target mRNA, resulting in post-transcriptional modifications that repress the translation of protein (14). microRNA-dependent gene regulation is a complex process, as one microRNA can regulate hundreds to thousands of genes (15). The ability for one microRNA to inhibit the expression of a large number of genes allows a single microRNA to repress several genes in a common biological pathway, resulting in robust regulation of an entire molecular process (16). Additionally, one gene can be targeted by multiple microRNA, resulting in cooperative / redundant regulation of a signal molecular process (15). This tight regulation that microRNA exert on cellular networks (17) suggests microRNA have may be an important mechanism controlling skeletal muscle plasticity (18).

Emerging evidence, suggest that altered expression of microRNA targets specific proteins that regulate carbohydrate metabolism. In cell culture experiments, miR-451 has been shown to target an upstream activator of AMPK, resulting in an inhibition of the AMPK signaling cascade (19). Elevation in miR-451 expression appears to be sensitive to glucose availability. When glucose concentrations are low, miR-451 expression is repressed, allowing for increased activation of AMPK (20). Conversely, with high glucose concentrations miR-451 expression is increased, resulting in diminished AMPK (20). Similarly microRNA have been shown to alter normal insulin signaling processes. Cell culture experiments have identified miR-33a/b and miR-126 as inhibitors of IRS (21, 22). Over expression of these microRNA reduce IRS protein content, resulting in insulin resistance and impaired glucose uptake (21, 22). Furthermore, in disease states that altered metabolic demands, such as diet-induced obesity and diabetes, dysregulation of microRNA expression has been observed, with specific microRNA (miR-29a, miR-34a, miR-103, miR-107, and miR-375) predicted to inhibit signaling proteins associated with insulin signaling upregulated (13). Findings from cell culture experiments and disease models indicate that microRNA contribute to regulation of carbohydrate metabolism.

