Our group recently found that microRNA which are highly enriched in skeletal muscle (i.e., myomiR) are sensitive to differing exercise modes with or without essential amino acid plus carbohydrate supplementation (unpublished data). In this investigation we found that weighted endurance-type exercise diminished miR-1-3p, miR-206, miR-208a-5p, and miR-499 expression, while conventional cycle ergometry endurance exercise increased microRNA expression. However, when cycle ergometry was combined with ingestion of essential amino acids plus carbohydrate, microRNA expression was either downregulated or remained the same immediately post and during the recovery phase, compared to baseline values. Divergent microRNA were all identified to target insulin signaling, with miR-206, miR-208-5p, and miR-499 were all predicted to target Akt, an intermediate signaling protein between IRS1 and AS160. These findings suggest that diminished microRNA expression immediately following exercise may have a functional role in mediating glucose uptake to replenish glycogen stores. Corroborating our findings, previous investigations have reported the microRNA acutely altered by exercise. Following an acute bout of endurance exercise there is diminished expression of miR-23, while mRNA expression of PGC-1 α and its downstream targets are upregulated (23, 24). When miR-23 is overexpressed in skeletal muscle there is a reduction in total PGC-1 α mRNA and protein content that results in reduced efficiency of mitochondrial function, an organelle crucial to cellular energy production (23). Furthermore, endurance exercise also downregulates miR-494, another inhibitor of PGC-1 α , allowing for increased gene expression of PGC-1 α and mitochondrial transcription factor A (25). While interventions have been conducted examining the relationship of microRNA expression to energy sensing genes in response to endurance exercise, no study has investigated the influence of altered glycogen availability in response to dietary manipulation on microRNA expression. Understanding how glycogen availability alters expression of microRNA will enable determination of their functional role in regulating carbohydrate metabolism to support energy availability to fuel physical performance.

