41 amplified using index-tagged primers to facilitate multiplexing. The amplified cDNA constructs will be size-
42 selected, quality controlled before loading to the NextSeq instrument to generate 50 base reads. Image
43 analysis and base calling will be performed using the Illumina pipeline.

44

45 Preprocessing of raw base calls, sample de-multiplexing, trimming and filtering will be similar to that
46 described in 'Analysis of sequencing output'. For the miRNA quantification/enrichment, reads are first
47 aligned to the Rfam RNA database to filter and profile other small RNA species in the samples. Then reads
48 are mapped for small RNA annotation against reference zebrafish mature mature RNA sequences from the
49 miRBASE database. The miRNA read count matrix for each sample will be generated using open source
50 tools such as PICARD.

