microRNA with significant changes in their expression will be uploaded to DNA Intelligent Analysis (DIANA)-miRPath 3.0 (Alexander Fleming Biological Sciences Research Center [BSRC], Athens, Greece; <http://diana.cslab.ece.ntua.gr>) to determine potential molecular pathways that these microRNA have previously been reported to regulate. Relevant Kyoto Encyclopedia of Genes and Genomes (KEGG; <http://www.genome.jp/kegg/>) pathways will be identified using experimentally verified targets from TarBase 7.0 (Alexander Fleming BSRC). Based on findings from this analysis, relevant gene and protein expression of relevant targets will be assessed.

Western Blotting

Approximately 30 mg of muscle will be homogenized in ice-cold buffer (1:10 wt/vol) containing 50 mM Tris-HCl (pH 7.5), 5 mM Na-pyrophosphate, 50 mM NaF, 1 mM EDTA, 1 mM EGTA, 10% glycerol (v/v), 1% Triton-X, 1 mM DTT, 1 mM benz-amidine, 1 mM PMSF, 10 μ g mL⁻¹ trypsin inhibitor and 2 μ g mL⁻¹ aprotinin. Homogenate will be centrifuged for 15 min at 10,000 \times g at 4°C. Protein concentration of supernatant (lysate) will be determined using 660 nm Protein Assay (ThermoFisher Scientific, Waltham, MA, USA). Phosphorylation status and total protein expression of molecular markers associated with carbohydrate metabolism will be determined using Western blot. Muscle lysates will be solubilized in Laemmli buffer, with equal amounts of total protein (15 μ g) separated by SDS-PAGE using precast Tris-HCl gels (Bio-Rad). Proteins will be transferred to polyvinylidene fluoride (PVDF) membranes and exposed to commercially available primary antibodies of intracellular markers involved with muscle metabolism to include but not limited to Akt, p-Akt^{Ser473}, AMPK α , p- AMPK α ^{Thr172}, PGC-1 α , SIRT1, ACC, p-ACC^{Ser79}, PDK4, IRS1, p-IRS1^{Ser302}, GSK-3 β , p-GSK-3 β ^{Ser9}, GSK-3 α , p-GSK-3 α ^{Ser21}, GLUT4 and PEPCK (Cell Signaling Technology, Danvers, MA, USA) at 4°C overnight. Labeling will be performed using secondary antibody (anti-rabbit IgG conjugate with horseradish peroxidase; Cell Signaling Technology), and chemiluminescent reagent will be applied (Super Signal, West Pico Kit; Pierce Biotechnology, Rockford, IL, USA). Blots will be quantified using a phosphoimager (ChemiDoc XRS; Bio-Rad) and Image

1 Lab software (Bio-Rad). To confirm equal protein loading per well a normalizing protein such as GAPDH or
2 β -actin will be assessed.
3

4 **Citrate Synthase Activity**

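### Pathways are read from the changed microRNAs alone, with no reference set of muscle-detected microRNAs, so the output cannot show that a pathway is specific to the carbohydrate response

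*Combined protocol and SAP*

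**What the plan says.** Section B5.4, Bioinformatics Analysis, states that "microRNA with significant changes in their expression will be uploaded to DNA Intelligent Analysis". The purpose is "to determine potential molecular pathways that these microRNA have previously been reported to regulate". Relevant KEGG "pathways will be identified using experimentally verified targets from TarBase 7.0". The output then has a use: "Based on findings from this analysis, relevant gene and protein expression of relevant targets will be assessed".

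The list comes from muscle. Under mRNA and microRNA Expression, small RNA from the biopsies is sequenced, and "The miRNA read count matrix for each sample will be generated using open source" tools. Only microRNAs that change significantly in muscle are then measured in serum, so the serum assays add no new candidates.

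Neither B5.4 nor B5.8.2 (Data analysis) gives the pathway step a reference set, a null comparison, a threshold or a multiplicity rule. B5.8.2 covers microRNA, mRNA and nutritional markers. Its general sentence on adjusting alpha does not mention pathways.

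Section B2 adds two facts about targeting: "one microRNA can regulate hundreds to thousands of genes", and "one gene can be targeted by multiple microRNA".

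**The concern.** Every candidate is a microRNA expressed in muscle. The relevant question is whether the changed microRNAs map to a pathway more than other microRNAs from the same muscle would. The planned query does not ask this. It asks which pathways have been reported for the list, and with broad, overlapping targeting almost any list will return the pathways that interest the investigators.

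At stake is the functional reading: that microRNAs responding to carbohydrate availability act on, say, insulin signalling. Muscle expression alone could produce that mapping. The output also steers which additional genes and proteins are measured.

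**Working it through.** The plan states no figure for this step, so there is none to reproduce. The documents supply only the order of magnitude of targets per microRNA (hundreds to thousands). All other inputs below are assumptions.

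**1. The step as written: look-up without a threshold.** Let G be the number of genes, P the genes in the pathway, t the targets per microRNA and k the list length. With targets spread evenly and independently, the chance that a random list has at least one target in the pathway is 1 − (1 − t/G)^(P·k). Take G = 15,000 and P = 140.

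- t = 100: one microRNA gives 1 − (1 − 100/15,000)^140 = 0.61; five give 1 − (1 − 100/15,000)^700 = 0.99.
- t = 200: 0.85 for one; above 0.99 for five.
- t = 500: 0.99 for one; above 0.99 for five.

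The result depends on t. If the verified database held only 20 targets per microRNA, five would give 1 − (1 − 20/15,000)^700 = 0.61 and ten 1 − (1 − 20/15,000)^1400 = 0.85. Clustering of targets on shared genes would also move these figures.

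**2. If the tool applies a whole-genome test.** Random lists were drawn from 250 simulated muscle microRNAs (median 500 targets, G = 15,000, P = 140). Each list was tested in two ways: with a hypergeometric test against all genes, and against 800 random same-size lists from the same 250. There were 500 test lists per scenario. The odds ratio is the assumed excess with which muscle microRNAs target pathway genes. Entries are the percentage of random lists called positive, for k = 5 / 10 / 20.

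| Odds ratio | All genes, p < 0.05 | All genes, p < 0.05/300 | Muscle reference, p < 0.05 |
|---|---|---|---|
| 1.0 | 5.8 / 2.6 / 2.2 | 0 / 0 / 0 | 6.0 / 4.2 / 3.6 |
| 1.25 | 34.0 / 41.6 / 58.2 | 1.2 / 3.4 / 4.6 | 3.8 / 5.8 / 7.6 |
| 1.5 | 64.6 / 96.2 / 98.8 | 7.4 / 29.8 / 59.8 | 4.8 / 8.0 / 5.8 |
| 2.0 | 97.2 / 100 / 100 | 58.6 / 92.2 / 99.6 | 7.0 / 2.2 / 3.8 |
| 3.0 | 100 / 100 / 100 | 99.6 / 99.8 / 100 | 4.2 / 4.0 / 3.4 |

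A second simulation used 20,000 genes, lists of 10, 500 targets each and a rate ratio in place of an odds ratio. It gave 4.1%, 25.0%, 77.8% and 99.7% at ratios 1.0, 1.2, 1.5 and 2.0. With 300 targets the figures were 4.0%, 19.2%, 60.7% and 96.9%; with 1,000 targets, 4.4%, 38.6%, 94.6% and 100%.

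**3. What the muscle reference does.** Its rate stays between 2.2% and 8.0% at every odds ratio. Around 5%, the standard error from 500 test lists is √(0.05·0.95/500) = 1.0 point and from 800 reference lists √(0.05·0.95/800) = 0.8 point, together about 1.2 points. The spread over 15 scenarios is therefore in line with noise.

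**The case against.** The strongest reply is that the plan claims little for this step. It names no enrichment test and speaks of potential pathways already reported, which is hypothesis generation. The tool's internal test and default background are not described, so any simulated error rate assumes how it behaves. All of this stands, and it limits the point to exploratory interpretation.

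A reader might infer four stronger things, none of which the documents support.

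- *Random muscle lists will usually be called positive in a formal test.* The high rates need excess targeting that no section documents. Without it the rate is nominal, and with Bonferroni over an assumed 300 pathways it is 0% at odds ratio 1.0 and 1% to 5% at 1.25.
- *The sponsor's own earlier data show non-specificity, because* "Divergent microRNA were all identified to target insulin signaling". In B2 the divergence lies between exercise and feeding conditions. The four named muscle-enriched microRNAs fell together after weighted exercise, which fits co-regulation at least as well. Three of them had predicted targets, whereas the present plan uses verified ones.
- *The pathway output decides what is assayed.* B5.4 already lists IRS1, AMPK, GLUT4 and others for mRNA, and Akt, IRS1, AMPK, GSK-3, GLUT4 and phospho-forms for Western blotting. The output can only add to these.
- *The main conclusions are at risk.* Neither hypothesis in B4 is a pathway claim, and the effect of carbohydrate is tested by the crossover model in B5.8.2.

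The gap itself is not answered. Measuring a pathway protein does not show that the pathway is specific to the changed microRNAs.

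**Conclusion.** The point holds as a modest one. As written, the look-up cannot separate carbohydrate-responsive microRNAs from any other muscle microRNAs. At 100 or more targets each, with 15,000 genes and a 140-gene pathway assumed, a random list of five touches the pathway with probability of at least 0.99. If a whole-genome test is used instead, the false-call rate runs from about 2% to 6% with no excess targeting to nearly 100% at an odds ratio of 2, and the documents do not say where in that range the truth lies. The consequence is confined to the pathway interpretation and the choice of additional targets. This is an inexpensive improvement to an exploratory step, not a threat to the primary comparison.

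**What to change.** Add to Bioinformatics Analysis, before the data are seen:

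- Define a detection filter for the muscle sequencing libraries, and name all microRNAs in the count matrix that pass it as the reference set.
- Fix the pathway list, the target database release and the test statistic.
- Run the same query on random sets of the same size from the reference set, and report an empirical p-value for each pathway, corrected across pathways.
- Choose the number of sets to suit the correction. With B sets the smallest p-value is 1/(B + 1). At B = 1,000 this is about 0.001, which can pass Bonferroni for at most 50 pathways (0.05/50 = 0.001). For about 300 pathways the threshold is 0.05/300 = 0.00017, so about 10,000 sets (smallest p about 0.0001) are suitable. False discovery rate control needs fewer, although 1,000 sets could then declare a pathway only if at least six reach the minimum together (6 × 0.05/300 = 0.001).
- Describe a pathway as linked to the carbohydrate-responsive microRNAs, and use it to prioritise additional targets, only if it passes. Report the others as not distinguishable from muscle background. Keep all pre-listed assays.

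No extra samples or visits are needed. The cost is a scripted resampling step and fewer pathways reported as specific. The documents do not say whether the web tool accepts batch queries. If it does not, the query would have to be reproduced offline from the same target and pathway tables.

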24 To complete testing on the 12 volunteers necessary to reach statistical power, we estimate we will need to
25 consent 44 individuals. All screening will stop once complete data has been collected on 12 volunteers.
26 Records and specimen collection are described in the Research Procedures and Data Collection sections.
27 During briefings and consenting potential participants will be informed that even though they may be
28 eligible and want to participate, if we are able to obtain enough data from preceding subjects, they may not
29 ultimately be tested.

30 **B5.2.3 Inclusion Criteria**

31 • Men and women aged 18 – 39 years
32 • Weight stable (± 5 lbs) for at least 2 months prior to the start of the study
33 • Body mass index (BMI) between 18.5-30 kg/m²
34 • Recreationally active based on assessment of physical activity history 2-4 days per week aerobic
35 and/or resistance exercise
36 • Refrain from taking any NSAIDS (i.e., aspirin, Advil®, Aleve®, Naprosyn®, or any aspirin-containing
37 product for 10 days before and at least 5 days AFTER each muscle biopsy. (*Tylenol® or
38 acetaminophen is ok to use if needed for discomfort)
39 • Refrain from the use of alcohol and nicotine for the duration of the study
40 • Females must be on contraception (e.g., oral birth control, NuvaRing®, Depo Provera®, etc.)
41 • Supervisor approved leave status for federal civilian employees working within the US Army Natick
42 Soldier Systems Center

[figure not shown]
43 **B5.2.4 Exclusion Criteria**

- 1 • Metabolic or cardiovascular abnormalities, gastrointestinal disorders (i.e., kidney disease, diabetes, cardiovascular disease, etc.)
- 2 • Disease or medication (i.e., diabetes medications, statins, corticosteroids, etc) that affects macronutrient utilization and/or the ability to participate in strenuous exercise
- 3 • Allergies or intolerance to foods (including but not limited to lactose intolerance/milk allergy), vegetarian practices, or medications (including, but not limited to, lidocaine or phenylalanine) to be utilized in the study
- 4 • Anemia (HCT < 38) and Sickle Cell Anemia/Trait
- 5 • Abnormal PT/PTT test or problems with blood clotting
- 6 • Present condition of alcoholism, use of nutritional/sports supplements, anabolic steroids, or other substance abuse issues
- 7 • Musculoskeletal injuries that compromise the ability to exercise
- 8 • Blood donation within 8 weeks of beginning the study
- 9 • Pregnancy
- 10
- 11
- 12
- 13
- 14
- 15
- 16
- 17
- 18

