Following identification of skeletal muscle microRNA that had a significant change, Taqman® probes (Applied Biosystems) will be used to assess the expression of these microRNA in serum to determine their potential use as noninvasive markers of altered carbohydrate metabolism following glycogen depletion and repletion. Total circulating miRNA will be extracted from 200 μ L serum using miRNeasy Serum/Plasma kit, which allows for extraction and purification of small (< 200 nt) cell-free RNA (Qiagen, Valencia, CA, USA). Exosomal circulating miRNA will also be extract from 1000 μ L serum using miRCURY™ RNA Isolation Kit to measure miRNA. To avoid introduction of potentially contaminating material, prior to RNA extraction serum samples will be centrifuged for 10 min at 4°C to remove cellular debris. Supernatant will be removed and transferred to a new tube without disturbing the pellet. Due to the small amount of RNA in the serum, 3.5 μ L of a Spike-In Control (C. elegans miR-39; Qiagen) will be added to all samples prior to extraction of RNA to determine the yield of template recovered. After extraction 3 μ L of serum RNA will be reverse transcribed using the TaqMan® microRNA RT kit (Applied Biosystems) with miRNA-specific stem-loop RT primers pooled in 1X-Tris-EDTA (TE) buffer for a final dilution of 0.05X. A pre-amplification step will be performed after reverse transcription to increase cDNA template using a primer pool of 20 X Taqman® Small RNA Assays (Applied Biosystems) for miRNA of interest at 0.05X concentration in 1X TE buffer. All serum miRNA will be normalized to the geometric of external (Spike-In Control C. elegans miR-39) and internal controls to allow for both technical and inter-individual normalization (47). Geometric mean of controls will be used to correct for possible outlying values and abundance differences between the different controls (48).

All reverse transcription for mRNA and miRNA, and pre-amplification of serum miRNA will be conducted in a T100™ Thermal Cycler (Bio-Rad, Hercules, CA). A StepOnePlus™ real-time PCR system (Applied Biosystems) will be used to perform all mRNA and miRNA analysis. Fold changes will be calculated using the $\Delta\Delta C_T$ method as described below in statistical analysis section.

Bioinformatics Analysis

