32 Hard copy data records will be stored for a minimum of three years from the time the study is completed.
33 Electronic data records will be maintained for a period of at least five years after the study has been
34 completed.
35

36 **B5.6 Managing Data and/or Human Biological Specimens for Future Research**

37 Any use of the samples outside of this defined protocol will be submitted as a protocol amendment or a
38 new protocol. Samples will be retained for future analyses once the protocol is closed if the subject
39 provided permission in the informed consent document.
40

41 **B5.8 Statistical Analysis**

42 **B5.8.1 Sample Size Estimation**

43 Statistical power and sample size were determined using the minimum fold change required for a
44 physiologically relevant difference in microRNA expression. Variance (standard deviation) was based
45 on recent publications assessing change in microRNA expression in skeletal muscle (18, 50, 51) and
46 circulating (34, 35, 52) in response to an acute bout of exercise. Using this information the sample
47 size necessary to determine statistical significance between intervention arms, with a mean fold
48

1 change of 1.5 ± 1 is 9 per group, with an alpha of 0.05 and 80% power. In the present study, 12
2 volunteers will be studied in a repeated measures crossover design to account for potential greater
3 inter-individual variability.
4

5 **B5.8.2 Data analysis**

7 Statistical analyses will be conducted using either SPSS (IBM Corp. Armonk, NY), SAS 9.3 (SAS
8 Institute Inc., Carey, NC), or equivalent. Common descriptive statistics will be used to describe
9 volunteer characteristics. Shapiro-Wilk tests will be used to determine normality of data. Mixed
10 model repeated measures ANOVA will be performed to determine main effects of time (baseline,
11 immediately, 3-hr, and 24-hr post glycogen depletion), carbohydrate intake ($6.0 \text{ g} \cdot \text{kg}^{-1} \cdot \text{d}^{-1}$ versus $1.5 \text{ g} \cdot \text{kg}^{-1} \cdot \text{d}^{-1}$) and time-by-carbohydrate interactions for skeletal muscle and circulating microRNA, mRNA
12 expression, and markers of nutritional status. If interactions are significant, Bonferroni correction will
13 be used to examine these relationships. Correlation coefficients and multiple regression analysis will
14 be used to evaluate relationships between study outcome measures. The alpha level will be adjusted

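### B5.8.1: the 9 per group fits a between-arm difference of 1.5 SD; 80% power for a 1.5-fold microRNA change is not supported without a high, unstated within-person correlation

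*Combined protocol and SAP*

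**What the plan says.** B5.8.1 (Sample Size Estimation) opens: "Statistical power and sample size were determined using the minimum fold change required for a" physiologically relevant difference in microRNA expression. The SD is taken from publications on microRNA change after acute exercise. The result is the sample "size necessary to determine statistical significance between intervention arms, with a mean fold" "change of 1.5 ± 1 is 9 per group, with an alpha of 0.05 and 80% power". The section then turns to the actual design: 12 "volunteers will be studied in a repeated measures crossover design to account for potential greater" variability between individuals.

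B5.8.1 does not state the scale of the fold change, the value that stands for no change, the test, its sidedness, whether the SD of 1 is per arm or of a within-person difference, or any within-person correlation.

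Three other places bear on the point:

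- B5.4 (mRNA and microRNA Expression) says that fold changes come from the delta-delta-CT "method as described below in statistical analysis section". Section B5.8 contains no such description.
- B5.8.2 plans a mixed "model repeated measures ANOVA will be performed to determine main effects of time (baseline" and three later time points), carbohydrate intake and their interaction, with alpha adjusted for multiple comparisons.
- B5.2.2 refers to the "12 volunteers necessary to reach statistical power".

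**The concern.** A fold change is a ratio. No change is 1 on the raw scale and 0 on a log scale, so a 1.5-fold change is a difference of 0.5, or log2(1.5) = 0.585. The stated 9 appears to come from entering the whole 1.5 as the difference between arms. That is an effect about three times as large as the one named on the raw scale (1.5 / 0.5), and about 2.6 times on log2 (1.5 / 0.585).

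This is the trial's only sample-size calculation, and the recruitment target rests on it. A reader will take the trial to have 80% power for a 1.5-fold change, and could then read a null result as evidence against a change of that size. Each volunteer has ten muscle biopsies, so what the study can detect should be stated correctly.

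**Working it through.** **Inputs.** From B5.8.1: 1.5, SD 1, alpha 0.05, power 80%, 9 per group, 12 in the crossover. Assumed because not stated: two-sided test; within-person correlation ρ, shown as a range. All powers use the noncentral t distribution.

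**Formulas.**
- Unpaired, n per group: noncentrality (δ/σ)·√(n/2), 2n − 2 df.
- Paired, n volunteers: SD of the difference = σ·√(2(1 − ρ)); dz = δ / that SD; noncentrality dz·√n, n − 1 df.
- The dz that gives 80% power is 1.156 at n = 8, 1.067 at n = 9 and 0.889 at n = 12. The correlation needed is ρ = 1 − (δ/σ)² / (2·dz²).

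**Step 1: reproduce the 9.** Unpaired with δ = 1.5, σ = 1: 79.7% at 8 per group, 84.8% at 9, so 9 is the minimum. Paired with δ = 1.5 and SD 1 per arm, 9 suffices from ρ = 1 − 2.25/(2 × 1.067²) = 0.01, and 8 suffices from ρ = 1 − 2.25/(2 × 1.156²) = 0.16. So 9 is also the paired minimum for ρ between about 0.01 and 0.16.

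**Step 2: can a 1.5-fold change give 9?** Unpaired at 9 per group with SD 1, power is 17% (δ = 0.5) or 21% (δ = 0.585); 80% would need 64 or 47 per group. Paired with SD 1 per arm, 9 is the minimum only for ρ of about 0.89 to 0.91 (raw) or 0.85 to 0.87 (log2).

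**Step 3: power of the design being run**, 12 volunteers, paired, for a 1.5-fold change:

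| Reading | ρ = 0 | 0.5 | 0.7 | 0.8 | ρ for 80% |
|---|---|---|---|---|---|
| Raw, δ = 0.5, SD 1 per arm | 20% | 35% | 53% | 70% | 0.84 |
| Log2, δ = 0.585, SD 1 per arm | 26% | 46% | 66% | 83% | 0.78 |
| Raw 1.5 ± 1 converted to lognormal | 32% | 56% | 78% | 91% | 0.72 |

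Third row: log-scale SD = √ln(1 + (1/1.5)²) = 0.606, or 0.87 on log2; δ/σ = 0.405/0.606 = 0.669; ρ = 1 − 0.669²/(2 × 0.889²) = 0.72.

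If 1 is already the SD of the within-person difference, no correlation enters: dz = 0.5 gives 35% and dz = 0.585 gives 46% with 12.

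**Step 4: the 1.5-unit reading with 12.** δ = 1.5, SD 1 per arm, ρ = 0: dz = 1.5/√2 = 1.06, power 92%.

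**Step 5: what 12 can detect.** 0.889 SD of the within-person difference (0.898 on 10 df if a period term is fitted). A 1.5-fold change therefore has 80% power if that SD is at most 0.585/0.889 = 0.658 log2 units (0.652 on 10 df), say 0.65.

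**The case against.** The best defence is that the arithmetic is sound. The stated inputs return exactly 9 with a standard unpaired t-test, and the text ties the 1.5 to the comparison between arms, so 1.5 may be the between-arm difference itself. A paired calculation with that difference also gives 9, at correlations just above zero. On this reading 12 crossover volunteers are ample. This stands: it would be wrong to call the figure an arithmetic slip.

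A reader might go further and infer that the trial is under-powered, citing the 17% or 21%. The documents do not support that. Those figures belong to 9 per group in parallel arms, which is not the design. The crossover can reach 80% if the correlation is high, and the source of the SD lies in cited publications that cannot be checked here. Nor is an SD of 1 on log2 given: converting a raw 1.5 ± 1 lowers the required correlation to about 0.72.

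The delta-delta-CT reference also does not fix the scale everywhere, because muscle microRNA is profiled first by sequencing, with no fold-change scale stated.

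None of this restores the claim as written. A 1.5-unit difference between arms is not a 1.5-fold change, and the text presents its figure as the minimum relevant fold change.

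**Conclusion.** The point holds as a mis-specified effect size and should be fixed. The 9 fits a between-arm difference of 1.5 SD. For a 1.5-fold change, each two-sided reading with a per-arm SD needs a correlation of about 0.72 to 0.84 with 12 volunteers. If the SD of 1 is already within-person, power is 35% to 46%. Nothing in the plan supplies the missing correlation or SD, so 80% power for a 1.5-fold change is unsupported, though not shown to be false.

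The result rests on a two-sided test and a single paired contrast at one time point. A one-sided test would lower the required correlations with 12 volunteers only to 0.79 (raw) and 0.71 (log2, SD 1 per arm). The alpha adjustment announced in B5.8.2 is not in the calculation, and any such adjustment would reduce power further.

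**What to change.** Keep 12 volunteers and replace the 9-per-group sentence in B5.8.1 with wording such as:

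> Twelve completers give 80% power (single paired between-arm contrast at one time point, two-sided alpha 0.05, before any multiplicity adjustment) for a difference of about 0.89 SD of the within-person difference in log2 expression change.

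Use 0.90 if a period term is added to the model. Then:

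- Claim 80% power for a 1.5-fold change only if a cited SD of the within-person difference is at most about 0.65 log2 units. Otherwise say that it is not established.
- If a 1.5-unit between-arm difference was intended, say so, give the scale and justify it as the minimum relevant effect. Then 9 stands as the computed minimum and 12 as the margin.

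Two minor consistency edits: in B5.2.2, refer to the 12 volunteers planned in B5.8.1 rather than to a number required for power; and add to B5.8.2 the delta-delta-CT definition that B5.4 promises.

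The cost is wording, plus a search for a supporting SD if the 1.5-fold claim is to stay. No participants, procedures or model terms need change. The downside is that the stated power may look less favourable.
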